## Abbreviations

SMM	Sexual minority man/men	
BSMM	Black sexual minority man/men	
HIV	Human Immunodeficiency Virus	
CVD	Cardiovascular disease	
CBT	Cognitive Behavior Therapy	

## **Study Protocol**

## 1. What the study will do

This study is a randomized controlled trial of Still Climbin', an 8-session cognitive behavior therapy (CBT) group intervention that addresses coping and medical mistrust among Black sexual minority men (SMM). Designed to be flexible for use in community settings, this intervention was developed in partnership with community stakeholders who emphasized the need for a community-based program outside of the health care system, without a specific disease focus. It intends to give Black SMM a safe space to receive support for the whole of their identity and to openly discuss barriers to health care. Participants will be followed for 12 months. The effectiveness of the Still Climbin' intervention will be assessed on health care engagement and receipt of evidence-based preventive care, through surveys administered at multiple points throughout the intervention period. These outcomes will be confirmed with information from medical records. The intervention is hypothesized to show increased health care engagement and receipt of evidence-based preventive care, in addition to better coping than the control group.

The Specific Aims is to conduct a randomized controlled trial to test the effects of *Still Climbin'*, a culturally congruent CBT group intervention, on the primary outcomes of healthcare engagement (e.g., at least one ambulatory care visit in the past 6 months) and receipt of evidence-based preventive care (e.g., chronic disease screenings) among Black SMM, and the secondary coping outcome.

#### 2. How it will be done

A total of 370 Black participants will be recruited; approximately half will be randomly assigned to receive the coping intervention and half to a no-treatment control condition. There will be about 10 cohorts of about 15 participants each for both intervention and control. Participants will be randomized to an intervention or control group after they complete the baseline survey. Participants will complete four surveys, starting with the baseline survey, and followed by 4-, 8-, and 12-month post-baseline follow-up surveys to assess health care engagement and receipt of evidence-based preventive care (e.g., cancer and diabetes screening, cardiovascular disease prevention, immunization, HIV prevention), and other topics such as coping strategies.

## 3. Why it is being done

This study's primary purpose is to address health issues that affect Black men, especially Black sexual minority men (SMM). Large racial/ethnic and sexual minority health and healthcare differences exist for preventable conditions in the U.S. Black men show higher mortality rates and lower healthcare engagement than nearly all other racial/ethnic subgroups. SMM, including Black SMM, are at high risk for poor physical health, including hypertension and cardiovascular disease (CVD), and have low access to care. Black SMM display high rates of HIV and other sexually transmitted infections. To date, there are no evidence-based prevention programs addressing overall health and wellness among Black sexual minority men; the few evidence-based interventions specifically tailored for Black SMM focus only on HIV.

## 4. How many people will be in the study?

We will enroll 370 participants at baseline. This sample size was determined in a priori power analyses to be sufficient to detect small to moderate intervention effect sizes for all primary and secondary outcomes.

## 5. Who is eligible to take part in it?

Eligibility criteria include: 18 years of age or older; Biologically male at birth; Identify as male; Self-identify as a Black/African American; Report having sex with men in the past 24 months; Anticipate being available for the next 12 months to attend study visits; Able to interact and communicate in written and spoken English.

## 6. What study therapy or other interventions will be given?

The intervention is an 8-session CBT group intervention that addresses coping with discrimination and medical mistrust among Black SMM in order to improve health care utilization, receipt of evidence-based care, and overall health and wellness.

#### 7. What tests will be done and how often?

We will administer surveys at baseline, and 4-, 8-, and 12-mont follow-up.

#### 8. What information will be collected

- 1. From baseline to 12-month post-baseline we will assess the Primary Outcome Measure: Proportion of Participants Who Have Inadequate Healthcare Utilization (self-reported). The survey will assess number of medical care visits in different settings (usual source of medical care, primary care visits, missed visits, urgent care, emergency department, hospital inpatient, residential care facility, hospital outpatient clinic, other type of clinic, dental care provider, home healthcare). We will construct measures of inadequate service utilization as having: (1) fewer than 1 ambulatory visit, (2) at least 1 emergency department visit (without subsequent hospitalization), or (3) at least 1 hospitalization in the past 6 months. Higher numbers of hospital visits and emergency department use likely results from not receiving indicated outpatient treatment, which can prevent complications, even among those who experience multiple chronic conditions.
- 2. From baseline to 12-month post-baseline we will assess the Primary Outcome Measure: Proportion of Participants Receiving Evidence-based Care Across Conditions and Assessments (self-reported). We will calculate receipt of evidence-based care as receipt of all eligible services within health condition categories (cancer screening, CVD prevention, immunization, diabetes care, HIV prevention, HIV treatment), and create an "all-or-none" measure across all categories.
- 3. From baseline to 4 months, to 8 months, and to 12 months, we will measure change the Secondary Outcome Measure, Adaptive Coping Strategies (Social Support Seeking; e.g., "I get emotional support from others"). Relevant items on the Brief Cope a general measure of coping strategies, will be adapted to assess frequency of use of each strategy, using the instructions, "indicate the extent you do what the item says when you are faced with discrimination," and response options 1 = "I haven't been doing this at all," 2 = "I've been doing this a little bit," 3 = "I've been doing this a medium amount" and 4 = "I've been doing this a lot."

Note: The study team originally planned to validate self-reported health care behaviors and outcomes with medical records data, but the grant was terminated before the team could collect these objective data.

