## 3. Detailed analyses of data items

Descriptive statistics will be performed on all study variables. We will transform any outcomes with skewed distributions (log or other as appropriate) to stabilize error variances and reduce the influence of outliers in regression models. To address potential bias from differential randomization and dropout, we will use covariates and non-response weights. Socio-demographic characteristics that significantly differ by intervention condition at will be included as covariates. Nonresponse weights will be used to address any potential differences between participants with complete data for at least one follow-up wave versus participants with only baseline data. Weights will be created using the inverse of the estimated probability of completing any follow-up survey, based on a multivariable logistic regression using socio-demographic and psychosocial variables that were not missing for any participant.

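### Read literally, the month-4 utilization report reaches about two months back before randomization, and the SAP neither states the scored window nor adjusts the primary model for baseline utilization

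*Combined protocol and SAP*

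**What the plan says.** Protocol section 8, item 1 introduces the outcome with "From baseline to 12-month post-baseline we will assess the Primary Outcome Measure: Proportion of Participants Who Have Inadequate Healthcare Utilization". It lists three ways to be inadequate: no ambulatory visit, an emergency department (ED) visit not followed by admission, "or (3) at least 1 hospitalization in the past 6 months". SAP section 4 repeats the three criteria in one parenthesis with the same look-back, and Protocol section 1 attaches it explicitly to the ambulatory criterion: "at least one ambulatory care visit in the past 6 months".

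On timing, Protocol section 2 states: "Participants will complete four surveys, starting with the baseline survey, and followed by 4-, 8-, and 12-month post-baseline follow-up surveys". It also states: "Participants will be randomized to an intervention or control group after they complete the baseline survey".

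On analysis:
- SAP section 4 specifies a logistic regression of a single yes/no for the whole of follow-up. It gives the coping model a term for baseline coping and gives the utilization model no such term.
- SAP section 3 sets the covariate rule: "Socio-demographic characteristics that significantly differ by intervention condition at will be included as covariates". Baseline utilization is not a socio-demographic characteristic.
- SAP section 3 bases the non-response weights on socio-demographic and psychosocial variables: "Weights will be created using the inverse of the estimated probability of completing any follow-up survey".
- SAP section 6 adds timepoint-specific and longitudinal comparisons of change in the primary outcomes, without naming a model.

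The survey wording is not in the documents. Nor is a rule for cutting the month-4 answer at randomization, or for combining the three follow-up reports.

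**The concern.** A six-month look-back asked at four months must reach past the start of the trial. ED visits and hospitalizations from before randomization would then count as follow-up events. An ambulatory visit from before randomization could hide the absence of any visit after it. Neither reflects the intervention, so any true difference in the month-4 report is diluted.

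The change comparison in SAP section 6 has a related problem. The baseline report covers months -6 to 0 and the month-4 report covers months -2 to 4, so an event in months -2 to 0 is counted at both times.

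At stake are the sensitivity of a primary outcome and the interpretation of the timepoint results. Part of a rise in effect from month 4 to month 8 could come from the window alone.

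**Working it through.** **The plan's own power figure.** The SAP gives none for utilization. Its figures concern coping and evidence-based care, and they reproduce at 120 per group with two-sided alpha 0.05 (assumed). The minimum detectable difference is (1.960 + 0.842) × √(2/120) = 0.362 SD, and power at 0.36 SD is 79.6%. The binary rows (5% + 11.0, 30% + 17.6, 60% + 16.8 points) give 79.8%, 80.3% and 80.3%. The 120 per group is carried forward below.

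**Windows.** A report at month m covers m - 6 to m, so the pre-baseline part is max(0, 6 - m).

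| Survey | Window (months) | Before baseline |
|---|---|---|
| Baseline | -6 to 0 | 6 of 6 |
| Month 4 | -2 to 4 | 2 of 6 (33%) |
| Month 8 | 2 to 8 | 0 |
| Month 12 | 6 to 12 | 0 |

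The follow-up reports together span 14 months, 2 of them (14%) before baseline. These are nominal values. A delay between the baseline survey and randomization adds to the two months; a late month-4 survey reduces them.

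**Illustrative dilution at month 4.** All rates are assumptions. Let p be the six-month risk of an ED visit or hospitalization, p0 the six-month probability of no ambulatory visit, r the rate ratio for ED/hospital events and k the rate ratio for visits. Events follow constant-rate, independent Poisson processes. Then P(inadequate) = 1 - P(no event) × P(at least one visit).

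Take p = 0.25, p0 = 0.30, r = 0.5, k = 1.5, with the effect starting at randomization.
- Control, any six-month window: 1 - 0.75 × 0.70 = 47.5%.
- Intervention, month 4 (2 untreated and 4 treated months): exponents (2 + 0.5×4)/6 = 4/6 and (2 + 1.5×4)/6 = 8/6, so 1 - 0.8255 × (1 - 0.2008) = 34.0%. Difference 13.5 points, power 57%.
- Intervention, month 8: exponents 0.5 and 1.5, so 1 - 0.8660 × (1 - 0.1643) = 27.6%. Difference 19.9 points, power 89%.

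The ratio is 13.5/19.9 = 0.68. Over p = 15, 25, 35%, p0 = 20, 30, 40% and (r, k) = (0.5, 1), (1, 1.5), (1, 2), (0.5, 1.5), 36 combinations in all, it runs from 0.64 to 0.82.

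**Later onset.** If the effect starts at month 2 (assumed), the same example gives 6.9 points at month 4 as written, 9.3 with a clean 0-4 window, and 19.9 at month 8. Most of the rise is then real.

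**Cutting the month-4 report to months 0-4.** Counting any inadequate report as yes (an assumed rule), with p = 0.25, p0 = 0.30 and an immediate effect, ever/never power at 120 per group is:

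| Effect | As written | Month 4 cut to 0-4 | Months 8 and 12 only |
|---|---|---|---|
| ED/hospital halved only | 23% | 21% | 30% |
| Visits × 1.5 only | 43% | 53% | 45% |
| Both | 93% | 96% | 96% |

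Over the 36 combinations, cutting to 0-4 changes power by -2.6 to +21 points. It is negative in 9, all with an effect on ED/hospital events only. Using months 8 and 12 alone changes power by -4 to +12 points.

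**Baseline adjustment.** Trials were simulated with both effects and gamma frailties of variance 0, 1 and 2 to represent persistence of use within men. Stratifying on baseline ED/hospital and no-visit status moved composite power from 93.0% to 93.2%, 62.3% to 68.7% and 37.9% to 48.9%. A separate run gave about 93% to 93%, 61% to 68% and 39% to 50%. Type I error was 4-6% in null simulations. The gain depends on how persistence is modelled and is smaller if one common propensity drives both components.

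**The case against.** The strongest objection is that the instrument is unseen. SAP section 4 limits the outcome to follow-up, so the month-4 item may ask only about time since baseline, and then no pre-randomization care enters. That stands as a limit. But the window would then be four months against a stated six, and no visit in four months is a different criterion from no visit in six. Nor can a six-month answer be split afterwards: the documents describe no event dates, and medical records were never collected because the grant was terminated.

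The opening words of item 1 in Protocol section 8 may describe when surveys are taken and not what they cover. That is fair; the conflict rests on SAP section 4.

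A reader might infer bias in favour of one arm, or an inflated false-positive rate. The documents do not support either: care before randomization is balanced in expectation, and the month-4 contrast remains a valid randomized comparison.

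A reader might also infer a definite loss of ever/never power by comparing the plan with a clean month 0-6 window. A survey at month 4 cannot deliver that window. The attainable one is months 0-4, and it can lower power as well as raise it.

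Nor can all growth from month 4 to month 8 be put down to the window. The programme has eight sessions, so an effect from day 0 is doubtful.

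Two further points stand in part. Baseline adjustment does not remove pre-randomization events. The reference to change in SAP section 6 leaves the use of baseline ambiguous, but it names no term and does not match the one model specified. Finally, the SAP calls 120 per group very conservative; with more men, a given dilution costs less power.

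**Conclusion.** The point holds as a gap in the specification of a primary outcome, with a likely but unquantified loss of sensitivity. On the documents' own schedule, a literal six-month report at month 4 is about one third pre-randomization, and no listed step removes that or uses baseline utilization. If the survey asks since baseline, the defect is instead an undeclared four-month window.

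The documents give no utilization rates, so no size follows from them. The 64-82% ratio rests on assumed rates and an immediate, constant effect. The change of about -3 to +21 points from cutting month 4 to months 0-4 also assumes 120 per group and that any inadequate report counts; its sign depends on which component responds. The plan should be amended, but the point does not invalidate the randomized comparison.

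**What to change.** 1. Adjust the primary utilization logistic regression for baseline utilization status. The baseline survey already collects it, so the cost is one covariate. The gain is nil if use does not persist within men and about 7 to 11 points of power in the simulations where it does. It leaves any pre-randomization events in the outcome.
2. State in the SAP the scored window for each survey and the rule that combines the three reports into one yes/no, consistent with an outcome defined over follow-up. Reconcile this with the change comparison in SAP section 6. The cost is text only.
3. Add a sensitivity analysis on the 8- and 12-month reports only (months 2-12), with non-response weights rebuilt for completing either one. It loses months 0-2 and men who answered only the month-4 survey, so it should not replace the primary analysis by default.
4. If the month-4 window is six months, report that comparison with a note that it includes about two pre-randomization months, and that part of any increase from month 4 to month 8 may come from the window.

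Counting month-4 ED/hospital events only in men with none at baseline could be explored. It should not be the primary definition: it starts the clock at different times for different men and leaves the ambulatory criterion uncorrected. None of these changes needs new data.

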## 4. Procedures and methods employed for analyzing the data

Analysis Plan. To test intervention effects under the Study Aim, we will use intention-to-treat analyses comparing intervention to control group outcomes. For inadequate healthcare engagement (<1 ambulatory visit, ≥1 emergency department visit, or ≥1 hospitalization in past 6 months) and receipt of evidence-based preventive care, we will conduct logistic regressions predicting whether participants had inadequate health care utilization or received evidence-based care within the entire follow-up period (yes/no). For coping, we will analyze all follow-up responses with repeated-measures linear regressions that include fixed effects for intervention condition, baseline value of the outcome, and covariates, employing a sandwich estimator to account for within-participant clustering; each participant can contribute up to three follow-up responses (from the 4-, 8-, or 12-month surveys).

Statistical Power. Based on our prior research, we anticipate medium effect sizes (0.5 SD). For analyses comparing intervention vs. control on continuous outcomes (e.g., coping) at follow-up, with a very conservative estimate of 240 participants (120 per group), there will be 80% power to

detect a difference of .36 SD (a small-to-medium effect size). For receipt of evidence-based preventive care, we used percentages from an analysis of our preliminary data, in which receipt of evidence-based care for CVD prevention and treatment ranged from 5.1% to 58.4% (and was lower for people living with HIV vs. people who were HIV-negative) [Ladapo JA, Richards AK, DeWitt CM, Harawa NT, Shoptaw S, Cunningham WE, Mafi JN. Disparities in the quality of cardiovascular care between HIV-infected versus HIV-uninfected adults in the United States: a cross-sectional study. J Am Heart Assoc. 2017;6(11):e007107. PubMed PMID: 29138182; PMCID: 5721786]. Thus, we estimated 80% power at 12-month follow-up to detect minimum between-groups difference representing small-to-medium effect sizes:

Control Group %	Minimum Detectable Difference	Effect Size (Cohn's D)
5%	11.0%	.37
30%	17.6%	.36
60%	16.8%	.36

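### Evidence-based care is compared between arms only as a yes/no, most naturally the all-or-none composite, so a null result could not separate no gain from partial gain

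*Combined protocol and SAP*

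**What the plan says.** Protocol section 8, item 2, builds the second primary outcome in two steps. The first is "receipt of all eligible services within health condition categories", for six categories running from cancer screening to HIV treatment. The second is to "create an 'all-or-none' measure across all categories".

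SAP section 4 gives the model. Logistic regressions will compare the arms on whether a man "received evidence-based care within the entire follow-up period (yes/no"). It does not say in so many words whether this yes/no is the cross-category composite or a category score.

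SAP section 6 mentions timepoint-specific and longitudinal models but names no other form of the outcome. Nowhere do the documents specify a count, a proportion of eligible categories met, or a category-by-category comparison between arms.

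The power table in SAP section 4 uses control rates drawn from cardiovascular care alone (5.1% to 58.4%). No expected rate for the composite is given.

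**The concern.** The measure is strict twice over: every eligible service within a category, then every eligible category. A man in the intervention arm who meets three of his four categories at follow-up is coded no, exactly like a man who meets none.

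The intervention works through coping and medical mistrust and, by Protocol section 1, has no specific disease focus. Partial gains spread over several kinds of care are therefore plausible, and the yes/no registers them only when they carry a man over the last hurdle.

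Two things are at stake. Power against a broad partial gain may be lower than it need be. And if the composite shows no difference, the planned output cannot tell a reader whether preventive care did not improve or improved without becoming complete. Nor would a positive composite show which kind of care changed.

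**Working it through.** **Inputs from the documents.** 120 per group (SAP section 4: "with a very conservative estimate of 240 participants (120 per group"), stated there for continuous outcomes; about 1:1 allocation (Protocol section 2); 80% power for 11.0, 17.6 and 16.8 points at control rates of 5%, 30% and 60%. The binary table states no sample size, and the plan states no significance level or sidedness. Two-sided 5% is assumed.

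**The plan's own figures.** With pooled variance under the null and no continuity correction,

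power = Φ[(Δ − 1.96·√(2p̄(1−p̄)/n)) / √((p₀(1−p₀)+p₁(1−p₁))/n)], n = 120.

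- 5% vs 16%: (0.110 − 1.96 × 0.0396)/0.0389 = 0.83, power 79.8%
- 30% vs 47.6%: (0.176 − 1.96 × 0.0629)/0.0619 = 0.85, power 80.3%
- 60% vs 76.8%: (0.168 − 1.96 × 0.0600)/0.0590 = 0.85, power 80.3%

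The table reproduces at 120 per group, so its arithmetic is sound. It applies to whatever yes/no rate is put in. If the composite lies near the 5% row, the share of men with complete care must more than triple (16/5 = 3.2) to reach 80% power.

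**A case that can be checked by hand.** Assume five independent items per man and a true gain from 50% to 60% in each.

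- All-or-none: 0.5⁵ = 3.1% vs 0.6⁵ = 7.8%. The formula gives (0.0465 − 1.96 × 0.0293)/0.0292 = −0.37, power about 35%.
- Number met: 2.5 vs 3.0. The SDs are √(5 × 0.5 × 0.5) = 1.12 and √(5 × 0.6 × 0.4) = 1.10, so the difference is 0.5/1.11 = 0.45 SD. Then 0.45 × √60 − 1.96 ≈ 1.5, power about 94%.

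Independence exaggerates the contrast, so correlation is added next.

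**Simulation with correlated categories.** Category scores come from a one-factor normal model, with 120 per arm. A two-proportion z-test on all-or-none is set against a z-test on the mean proportion of categories met. The number of categories, rates, gains and latent correlations are all assumptions.

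| Assumed setting | Correlation | All-or-none power | Proportion-met power |
|---|---|---|---|
| 4 categories, 50% → 60% each (composite 11% → 19% at 0.2) | 0.2 | about 42% | about 76% |
| Same | 0.4 | about 39% | about 65% |
| 3–5 categories, control 40–60%, +10 points each | 0.2 and 0.4 | 27–55% | 59–85% |
| 4 categories, 80% → 90% each | 0.2 | 94% | 98% |
| Same | 0.4 | 89% | 93% |
| 3 categories at 85% in both arms, one moving 40% → 60% | 0.2 | 54% | 40% |
| Same | 0.4 | 59% | 33% |

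As a check on the first row, the closed formula with 11% vs 19% gives (0.08 − 1.96 × 0.0461)/0.0458 = −0.23, power 41%.

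**Unequal eligibility.** Letting men differ in the number of eligible categories (two to five, 50% control, +10 points) gave about 38–39% for all-or-none and 60–69% for the proportion met. Adjusting the all-or-none model for the number of eligible categories added 0–3 points of power.

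**The case against.** The best defence is that all-or-none is a deliberate, openly named standard. It asks whether a man received all the care he was eligible for, which is a coherent question. That stands, and nothing here says the primary outcome is wrong.

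Four stronger readings are tempting, and the documents do not support them.

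- *A real gain would probably be reported as no effect.* This depends on the scenario. The low power figures come from a uniform 10-point gain at 40–60% control receipt. Ten points per category is a modest effect: in the four-category, 50% setting, a 15-point gain gives all-or-none about 75–78% power and 17.5 points about 87–89%. At 80% receipt the two measures are close, and with a single bottleneck category all-or-none does better. The documents do not say which case applies.
- *Category scores are never to be compared by arm.* SAP section 4 does not confine its regressions to the composite, and power rates taken from one category would fit category-level models. What can be said is that no such comparison is specified.
- *A partial gainer is counted as unchanged.* SAP section 6 speaks loosely of change, but the section 4 model for this outcome uses status over follow-up. He is simply coded no.
- *Men eligible for more categories face a higher bar, which biases the comparison.* Under randomization the number of eligible categories is balanced in expectation. Adjusting for it is a matter of precision.

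It is also fair to note that SAP section 2 restricts the analyses to primary and secondary outcomes after early termination, and that the documents do not show whether outcomes have already been examined by arm. A supportive analysis of a primary outcome falls within that restriction, but whether it can be called pre-specified depends on timing.

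**Conclusion.** The point holds as a gap in specification and interpretation. The plan calculates category scores, but the only evidence-based-care contrast it specifies is a yes/no, most naturally the composite. A broad partial gain may therefore be missed, and a null composite would be ambiguous.

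Under the assumed uniform 10-point gain at 40–60% control receipt, with three to five categories and latent correlation 0.2 or 0.4, the power is 27–55% against 59–85%. That range is illustrative: it rests on category rates and correlations that the documents do not supply, the difference narrows to about 4 points at 80% receipt, and the bottleneck case reverses it. The published power figures are reproduced and are not in dispute. This is an inexpensive improvement to the analysis plan, and leaves the primary outcome as it is.

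**What to change.** In SAP section 4:

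1. Keep all-or-none as the primary outcome, and state that the logistic regression models this cross-category composite.
2. Add the number of categories for which a man is eligible at baseline as a covariate in that model, giving precision as the reason.
3. Add one analysis labelled supportive: the proportion of eligible categories met per man, compared by arm using linear regression with a robust variance. Fix it before outcomes are compared by arm; if they already have been, label it post hoc.
4. Report each category's rate by arm among the men eligible for it, with confidence intervals, labelled descriptive.

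The category scores are already part of the plan, so no new data are needed. The cost is some SAP wording, a few table rows and one more contrast, which must be clearly marked so that it is not taken for a third primary outcome.
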